2.2.1. Nonclinical Overview

The pharmacology and safety of PF-07242813 are supported by nonclinical studies.

2.2.1.1. Nonclinical Pharmacology

In vitro assessments using several methods have demonstrated that PF-07242813 binds to both human and cynomolgus monkey CD1a with similar high affinity. SPR analysis demonstrated high affinity binding to recombinant forms of both human and cynomolgus monkey CD1a. Flow cytometry studies showed that PF-07242813 bound surface-expressed human and cynomolgus monkey CD1a, whether exogenously expressed by transfection into CHO cells or endogenously expressed on monocyte-derived dendritic cells. PF-07242813 suppressed IL-2 secretion and upregulation of CD69 expression on Jurkat76-BK6 cells, a CD1a-restricted T cell line, during co-culture with human CD1a expressing cells. In vitro, IL-17A secretion by primary CD3⁺ cells, isolated from either whole blood or healthy skin, in response to CD1a stimulation was suppressed by PF-07242813. Likewise, PF-07242813 was able to suppress IL-17A secretion by primary cynomolgus monkey CD3⁺ cells when co-cultured with cells expressing cynomolgus monkey CD1a.

Additionally, PF-07242813 was shown functionally to neutralize CD1a-dependent immune responses *in vivo* using human CD1a transgenic mice with an HDM-induced model of skin inflammation. PF-07242813, when administered *in vivo* in a prophylactic dosing regime, resulted in a statistically significant decrease of all AD measurements assessed, including dermatitis score, total IgE levels, HDM-specific IgE titers, presence of inflammatory or IL-13⁺ cells in the skin, and presence of an AD gene signature in the skin.

Taken as a whole, these data demonstrate PF-07242813 neutralizes CD1a-dependent T cell activation and inflammation supporting its development as a novel therapeutic for the treatment of AD.

2.2.1.2. Nonclinical Safety

No test article-related effects or target organs were identified following once weekly administration of PF-07242813 to cynomolgus monkeys for 13 weeks in the GLP toxicity study that would predict a safety risk for participants in early clinical studies. The NOAEL in the pivotal 13-week monkey toxicity study was the highest dose tested, 200 mg/kg/week (IV), with C_{max} and C_{av} exposures of 10200 µg/mL and 6310 µg/mL, respectively.

Staining of neuroendocrine cells with PF-07242813 in the human pituitary was observed in the TCR study. However, the risk of pituitary toxicity is considered low since CD1a is not expected to be expressed in the pituitary, PF-07242813 does not have effector function, and no toxicity was observed in the 13-week repeat-dose monkey study for other tissues that showed positive staining in the TCR study.

The in vitro cytokine release assay identified the potential for PF-07242813 to induce cytokine release; however, the clinical translation of findings from this assay has not been established.

[figure not shown]
[figure not shown]
[figure not shown]
The nonclinical program supports the progression of PF-07242813 in clinical trials of up to 3 months in duration via the SC and/or IV routes of administration.

2.2.1.3. Nonclinical PK

[figure not shown]
Non-linear PK was observed after a single IV dose in cynomolgus monkeys, consistent with TMDD. In the pivotal repeat-dose GLP study, there were no apparent sex-related differences in systemic exposure (as assessed by C_{max} and AUC), and systemic exposure increased with increasing dose and was higher after repeat dosing. **CCI**

The PK of PF-07242813 in humans are expected to be the same as those of a typical therapeutic IgG mAb. Based on a site of action PK/PD model, the predicted efficacious dose of PF-07242813 in humans is 30 mg SC Q4W. The predicted steady-state human AUC_{tau} for the efficacious dose level is 1730 $\mu\text{g}\cdot\text{h}/\text{mL}$ and the predicted C_{max} and C_{av} values are 3.67 and 2.58 $\mu\text{g}/\text{mL}$, respectively.

CCI

2.2.2. Clinical Overview

PF-07242813 has not been administered to humans. Therefore, there are no clinical safety data.

2.3. Benefit/Risk Assessment

Study C4461001 is the first time that PF-07242813 will be administered to humans. For healthy participants participating in this single and multiple doses, no clinical benefit is expected. The purpose of the study is to provide the basis for further clinical development of PF-07242813 as a potential new, pharmacological agent for the treatment of participants with AD. As to date, no specific human risks have been identified; postulated risks based on nonclinical studies are summarized in [Section 2.2.1](#). The clinical impact of these potential risks will be minimized through the proposed cautious dose. The clinical impact of these potential risks will be minimized through the proposed cautious dose escalation process wherein higher doses of PF-07242813 will be administered only after lower doses have been found to be well tolerated with an acceptable safety profile. In addition, this study includes standard, intensive, inpatient monitoring of the participants following administration of single and multiple doses of the study intervention.

The risk assessment for study participation and potential risks of PF-07242813 is provided below. More detailed information about the known and expected benefits and risks and reasonably expected AEs of PF-07242813 may be found in the Investigator's Brochure, which is the SRSD for this study.

2.3.1. Risk Assessment

CCI

CCI					
Study Procedures					
CCI					

2.3.2. Benefit Assessment

No clinical benefit is anticipated for healthy participants. However, participants may benefit society by contributing to the process of developing new therapies in an area of unmet need. Additionally, participants will benefit from Medical evaluations/assessments associated with study procedures (eg, physical exam, ECG, labs, etc.).

Similarly, while no clinical benefit may be expected for participants with AD, they may obtain potential benefit of receiving study intervention during study duration that may have clinical utility.

2.3.3. Overall Benefit/Risk Conclusion

Based on the preclinical toxicology studies, measures taken to minimize risk to participants in this study, and the ultimate potential benefit of PF-07242813 to patients with AD, the overall potential benefit/risk of PF-07242813 is favorable.

3. OBJECTIVES, ENDPOINTS, AND ESTIMANDS

3.1. Objectives and Endpoints: Part 1 (Healthy Adult Participants)

Objectives	Endpoints
Primary: To evaluate the safety and tolerability of PF-07242813, following single and multiple doses in healthy adults.	Primary: Incidence of treatment-emergent adverse events (AEs and SAEs); vital signs, safety laboratory tests, cardiac telemetry (SAD only), and ECG.
Secondary: To characterize the serum exposure of PF-07242813, following single and multiple doses in healthy adults.	Secondary: PF-07242813 serum exposure as data permit: AUC_{last} , AUC_{inf} , C_{max} , T_{max} and $t_{1/2}$ after single doses; AUC_{τ} , C_{max} , and T_{max} after each repeated dose; and $t_{1/2}$ after the last repeated dose.
CCI	

3.2. Objectives, Endpoints and Estimands: Part 2 (Atopic Dermatitis Participants)

Objectives	Endpoints	Estimands
Primary:	Primary:	Primary:
To evaluate the safety and tolerability of PF-07242813 versus placebo, in participants with moderate to severe AD.	Incidence of treatment-emergent adverse events (AEs and SAEs); vital signs, safety laboratory tests, and ECG.	There is no defined estimand for these endpoints; they will be analyzed using CaPS as applicable.
Secondary:	Secondary:	Secondary:
To compare the efficacy of PF-07242813 versus placebo on percent change from baseline in Eczema Area and Severity Index (EASI) in participants with moderate to severe atopic dermatitis (AD).	Percent change from baseline in EASI total score at Week 6.	
Estimand E1: This estimand is intended to provide a population level estimate of the treatment effect of the study intervention on a continuous endpoint; without prohibited medications during treatment.
 
Study Intervention: PF-07242813 or placebo.
 
Population: Participants with moderate to severe AD as defined by the inclusion and exclusion criteria.
 
Variable: Percent change from baseline in EASI total score at Week 6.
 
Intercurrent Events:
 
a. Prohibited medications – all scores in participants who receive prohibited medication post randomization to Week 6 will be omitted from the analysis and treated as missing scores. Missing scores will be imputed based on the assumption that participants do not benefit from the study intervention.b. Inadequate compliance – participants data will be used as recorded. 
Events a and b are stated with precedence in descending order.
 
Population level summary:
 
The percent change from baseline mean difference between PF-07242813 and placebo in EASI score.

PFIZER CONFIDENTIAL

PFIZER CONFIDENTIAL

Objectives	Endpoints	Estimands
	CC1 [REDACTED]	

4. STUDY DESIGN

4.1. Overall Design

This is a first-in-human (FIH) study of PF-07242813 that will be conducted in 2 parts: Part 1 will be conducted in healthy adult participants and Part 2 will be conducted in adult participants with moderate to severe AD (see [Figure 1](#)).

Up to approximately 145 participants will be randomized to the study: in Part 1, up to approximately 57 healthy participants in SAD (including 5 Japanese participants), up to approximately 40 healthy participants, including an optional cohort in MAD, and in Part 2 up to 48 participants with moderate to severe AD.

4.1.1. Part 1: Single and Multiple Ascending Dose in Healthy Participants

Part 1 is within-cohort randomized, participant- and investigator- blind, sponsor-open, and placebo-controlled investigation of the safety, tolerability, PK, and immunogenicity following SAD and MAD of PF-07242813.

Approximately 97 healthy adult participants will be enrolled at a single study site into the proposed cohorts listed below. Participants may only participate in one cohort.

Participants in the single dose cohorts will be randomized sequentially as follows:

- Cohort 1 (n=4): 0.3 mg active (n=2) or placebo (n=2), IV;
- Cohort 2 (n=4): 1 mg active (n=2) or placebo (n=2), IV;
- Cohort 3 (n=4): 3 mg active (n=2) or placebo (n=2), IV;
- Cohort 4 (n=8): 10 mg active (n=6) or placebo (n=2), IV;
- Cohort 5 (n=8): 30 mg active (n=6) or placebo (n=2), IV;
- Cohort 6 (n=8): 100 mg active (n=6) or placebo (n=2), IV;
- Cohort 7 (n=8): 300 mg active (n=6) or placebo (n=2), IV;
- Cohort 8 (n=8): 1000 mg active (n=6), or placebo (n=2), IV.

Participants in the multiple dose cohorts, will be randomized as follows:

- Cohort 10 (n=8): 15 mg active (n=6) or placebo (n=2), SC x 3 doses Q2W;
- Cohort 11 (n=8): 50 mg active (n=6) or placebo (n=2), SC x 3 doses Q2W;
- Cohort 12 (n=8): 150 mg active (n=6) or placebo (n=2), SC x 3 doses Q2W;
- Cohort 13 (n=8): 300 mg active (n=6) or placebo (n=2), SC x 3 doses Q2W;
- Cohort 14 (n=8, optional): ≤ 1000 mg IV active (n=6) or placebo (n=2), SC x 3 doses Q2W.

The Japanese Participant Cohort will be randomized as follows:

- Cohort 15 (n=5): a single IV dose active (n=4) or placebo (n=1).

Within 28 days of successful completion of the screening process, eligible participants will be randomized to receive a single IV infusion of PF-07242813 or placebo. In order to mitigate any unanticipated acute safety risks within the IV infused SAD cohorts, sentinel dosing will be implemented in all SAD cohorts (ie, cohorts where the dose being tested is the highest administered in the study to date). For sentinel dosing, the first 2 participants (1 active: 1 placebo) will be dosed prior to the remaining participants in the cohort and monitored for at least 24 h to assess safety. If the dose level for the first 2 sentinel participants is determined to have an acceptable safety and tolerability profile, as judged by the investigator, the remaining participants within the cohort will be dosed. Single dose cohorts will be enrolled sequentially in a dose escalating fashion starting from the lowest proposed dose (0.3 mg). During the SAD period, escalation to subsequent dose levels will occur following the sponsor's review of available safety through study Day 8 and PK data through Day 3 for the previous cohort. There will be a minimum of 10 days between cohorts for dose escalation. Dosing in this part (up to the maximum dose of 1000 mg IV) may be adjusted depending upon the actual exposure of PF-07242813 observed in humans at lower doses. If, based on the observed data, the subsequent dose projected group mean C_{max} is $> 1020 \mu\text{g/mL}$ or $AUC_{168H} > 106000 \mu\text{g.h/mL}$, the exposure limits determined as 1/10th of the mean exposures observed at NOAEL in the 13-week cynomolgus monkey toxicity study, that dose will not be explored.

Participants will be admitted into the clinic approximately 1 day prior to dosing and be required to stay overnight in the study center through completion of Day 5 evaluations. Participants in the single dose cohorts will return for outpatient visits per the [Schedule of Activities \(Table 1\)](#), up to Day 71 visit (or at least 4 half-lives of PF-07242813 based on observed data). For Cohort 1, the outpatient visit is up to Day 29 (± 3 days). For Cohorts 2 and 3, the final out-patient visit will be determined based on emerging safety and PK data from previous cohort(s). As such, the final scheduled visit may be earlier than Day 71 (± 3 days), but will be at least through Day 29 (± 3 days).

Four (4) multiple SC dose cohorts of PF-07242813 (15 mg to 300 mg) and 1 optional multiple IV dose cohort in healthy participants are planned. Initiation of the multiple dose (Cohort 10) will occur following the Sponsor's review of available safety data through study Day 8 and PK data through study Day 3 from Cohort 6 (100 mg single IV dose) and the accumulated safety from the previous single dose cohorts. The starting dose of 15 mg for the initial multiple dose cohort may be adjusted, based on emerging safety and PK data from the single dose cohorts. Progression to the next multiple dose may proceed after review of:

- Safety/tolerability data through Day 8 and PK data through Day 3 of the single dose that is no lower than the planned SC dose in next MAD cohort;
- Cumulative safety and PK data from the previous single dose cohorts;
- Safety/tolerability data through Day 22 (7 days following the 2nd dose) of the ongoing MAD cohort and previous MAD cohorts with lower doses.

If, based on the observed data, the subsequent dose in next cohort projected group mean C_{max} is $>1020 \mu\text{g}/\text{mL}$ or $AUC_{168H} > 106000 \mu\text{g} \cdot \text{h}/\text{mL}$ following the 3rd dose, that dose will not be explored. The 5th MAD cohort (**Cohort 14**) is optional for further investigation of multiple doses as needed. The dose level for this cohort will be determined following a review of the cumulative safety and PK data up to 1000 mg IV single dose cohort and at least through Day 22 (7 days following the 3rd dose) of the ongoing 300 mg MAD cohort. The dose in this cohort will be no more than 1000 mg IV.

Healthy participants who are enrolled into the multiple dose cohorts will be randomized to receive PF-07242813 or placebo every 2 weeks (Q2W) for a total of 3 doses. Participants will be confined to the clinical research unit starting on the day prior to dosing and through at least 96 hours after the first dose of study intervention and 48 hours after the second and third doses. Participants may remain in house longer at the discretion of the PI due to operational logistics. Participants will return for outpatient visits per the ([Table 2](#)), at least through Day 99 visit (or at least 4 half-lives of PF-07242813 based on observed data). Based on emerging PK data, additional samples may be added to ensure PK is adequately characterized. Based on emerging data from previous and ongoing single and multiple dose cohorts, doses planned may be modified and other doses and/or dosing regimens (eg, Q4W) may be explored. If the exposures in the subsequent dose is projected to exceed the exposure limits pre-specified, after repeat doses, that dose will not be explored.

In addition, a cohort of healthy Japanese adults (Cohort 15, n=5) will be enrolled to receive a single IV administration of PF-07242813 or placebo (4 on PF-07242813 and 1 on placebo). This cohort will be initiated after single dose escalation in healthy participants (SAD) is complete and will enroll in parallel to Part 2.

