Sample(s) CCI of hormone levels: HGH, IGF-1, TSH, T4 and Cortisol ^j	XX	XX	XX							XX					
Banked Biospecimens for Biomarkers Prep B2.5		X								X					
Adverse event monitoring	X	X	X	X	X	X	X	X	X	X	X	X	X	X	X

- a. Study procedures may be performed Day-1, or prior to first dose on Day 1.
- b. Procedures should be completed within ±10% of the collection time (ie, 2 hours ±12 minutes; 6 hours ±36 minutes, etc).
- c. A full PE may be done at screening or may be deferred to Day -1 at the discretion of the principal investigator. A limited PE may be performed at discharge at the discretion of the investigator. A limited PE may also be performed at the discretion of the investigator at a follow-up visit if there is a new or ongoing AE.
- d. FSH test is performed only in WONCBP at screening to confirm postmenopausal status in females who have been amenorrhoeic for at least 12 consecutive months.
- e. Infusion pertains *only* to the IV cohort and does not pertain to the SC Cohorts.
- f. ECGs will be collected in triplicate approximately 2-4 minutes apart at pre-dose, and during clinical confinement at the times specified above. Single ECGs will be collected at all other designated visits.
- g. Vital signs include supine blood pressure, pulse rate, respiratory rate, and temperature.
- h. If not collected on the designated collection day, collect at the next available time point when biospecimens are being collected in conjunction with a participant visit.
- i. Pregnancy test is performed only in WOCBP.
- j. Hormone samples will be collected in the morning. Beginning at baseline visit (Day -1 or predose Day 1), samples should be collected at approximately the same time in the morning.

Day 14 Through Day 22 Visits (2nd Dose)

Visit Identifier	Clinical Confinement								Out-patient Visit	Early Termination
	Study Day	Day 14	Day 15				Day 16	Day 17	Day 19	
Hours After Dose (for clinical confinement portion)		-2 hrs to -5 min	0	End of infusion ^{a,b}	2 ^a	6 ^a	12 ^a	24 ^a	48 ^a	96 ^a
Admission to Clinical Research Unit	X									
Physical examination ^c										X
Laboratory (hematology, blood chemistry, urinalysis)	X						X		X	X
Urine Drug Test	X									
Urine Pregnancy Test ^f	X									X
12Lead -ECG ^d		X		X	X	X	X	X	X	X
Vital Signs ^e		X		X	X	X	X	X	X	X
Prior/Concomitant Medication	X	X	X	X	X	X	X	X	X	X
Study Intervention Administration			X							
Infusion/Injection Site Reaction				X	X	X	X	X		
Pharmacokinetic (PK) blood sampling		X		X	X	X	X	X	X	X
CCl										

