Sample(s) for CCl of hormone levels: HGH, IGF-1, TSH, T4 and Cortisol ^g										
Banked Biospecimens for Biomarkers Prep B2.5	X						X			
Adverse event monitoring	→	→	→	→	→	→	→	→	→	X
Discharge from Clinic								X		

- Procedures should be completed within ±10% of the collection time (ie, 2 hours ±12 minutes; 6 hours ±36 minutes, etc).
- Infusion pertains *only* to the IV cohorts and does not pertain to the SC Cohorts.
- Physical examination prior to the second dose will be at the discretion of the investigator, based on any review of potential adverse events or other clinical signs/symptoms.
- ECGs will be collected in triplicate approximately 2-4 minutes apart at pre-dose, and during clinical confinement at the times specified in the [Schedule of Activities](#) (Day 15 prior to dose and up to 48 hours post-dose). Single ECGs will be collected at all other designated visits.
- Vital signs include supine blood pressure, respiratory, pulse rate, and temperature.
- Pregnancy test is performed only in WOCBP.
- Hormone samples will be collected in the morning, at the same time of day.

Day 28 Through Day 99 Visit (3rd Dose)

Visit Identifier	Clinical Confinement								Day 30	Day 31	Day 33	Day 36 ±1	Day 43 ±3	Day 57 ±3	Day 71 ±3	Day 85 ±3	Day 99 ±3	EOS	Early Termination
	Study Day	Day 28	Day 29																
Hours After Dose (for clinical confinement portion)		-2 hrs to -5 min	0	End of infusion ^{a,b}	2 ^a	6 ^a	12 ^a	24 ^a	48 ^a	96 ^a									
Admission to Clinical Research Unit	X																		
Physical Examination ^c																		X	X
Laboratory (hematology, blood chemistry, urinalysis)	X									X			X		X			X	X
Urine Drug Test	X																		
Urine Pregnancy Test ^f	X														X			X	X
12-Lead ECG ^d		X		X		X	X	X	X			X	X	X	X	X	X		X
Vital Signs ^e		X		X		X	X	X	X			X	X	X	X	X	X		X
Prior/Concomitant Medication	X												X	X	X	X	X	X	X
Study Intervention Administration			X																
Infusion/Injection Site Reaction				X	X	X	X	X	X										
Pharmacokinetic (PK) blood sampling		X		X	X	X	X	X	X	X	X	X	X	X	X	X	X		X
CCI [REDACTED]			[REDACTED]															[REDACTED]	[REDACTED]
Sample(s) for CCI of hormone levels: HGH, IGF-1, TSH, T4 and Cortisol ^g			[REDACTED]					[REDACTED]											
Banked Biospecimens for Biomarkers Prep B2.5	X								X										
Adverse event monitoring	→	→	→	→	→	→	→	→	→	→	→	→	→	→	→	→	→	X	X
Discharge from Clinic										X									

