- Procedures should be completed within ±10% of the collection time (ie, 2 hours ±12 minutes; 6 hours ±36 minutes, etc).
- Infusion pertains *only* to the IV cohort and does not pertain to the SC Cohorts.
- Physical examination prior to the third dose will be at the discretion of the investigator, based on any review of potential adverse events or other clinical signs/symptoms.
- ECGs will be collected in triplicate approximately 2-4 minutes apart pre-dose, and during clinical confinement at the times specified in the **Schedule of Activities** (Day 29 prior to dose and up to 48 hours post-dose). Single ECGs will be collected at all other designated visits.
- Vital signs include supine blood pressure, respiratory rate, pulse rate, and temperature.
- Pregnancy test is performed only in WOCBP.
- Hormone samples will be collected at the same time of day, in the morning.

Table 3. Part 2. Schedule of Activities in AD Participants – Cohort 9

Visit Identifier	Screening	Week 1	Week 2	Week 3	Week 4	Week 6	Week 8	Week 12	EOS Week 16	ET
Day relative to dose (Day 1)	Day-28 to Day-2	Day 1	Day 8	Day 15	Day 29	Day 43	Day 57	Day 85	Day 113	
Visit Window - Days			±3	±3	±3	±3	±3	±3	±3	
Screening Assessments										
Informed consent	X									
Demography	X									
Medical History (including AD)	X									
Height	X									
Body Weight	X	X ^a								
Drug, Alcohol and Tobacco History	X	X ^a								
FSH ^d	X									
HIV, HBsAg, HBcAb, HCVAb	X									
QuantiFERON TB Gold	X									
Inclusion/Exclusion	X	X								
Randomization		X ^a								
Laboratory Assessments										
Safety labs (hematology, blood chemistry, urinalysis)	X	X ^b	X		X	X	X	X	X	
Urine Drug Test	X	X ^a								
Pregnancy test ^d	X	X			X		X	X	X	
PK blood samples		X ^b		X	X	X	X	X	X	
CCI										
Medical Procedures										
Physical Examination ^c	X								X	X

Visit Identifier	Screening	Week 1	Week 2	Week 3	Week 4	Week 6	Week 8	Week 12	EOS Week 16	ET
Day relative to dose (Day 1)	Day-28 to Day-2	Day 1	Day 8	Day 15	Day 29	Day 43	Day 57	Day 85	Day 113	
Visit Window - Days			±3	±3	±3	±3	±3	±3	±3	
12 Lead -ECG ^f	X	X ^{b,f}	X	X	X	X	X	X	X	X
Spirometry (FEV1, FVC) ^k	X			X	X	X	X	X	X	X
Vital Signs ^g	X	X	X	X	X	X	X	X	X	X
Exploratory Biomarker										
Banked Biospecimens for Genetics Prep D1 ^h		X ^a								
Banked Biospecimen -Prep PBMC2		X ^a	X			X		X	X	X
Banked Biospecimen -Prep R1		X ^a	X			X		X	X	X
Banked Biospecimens for Biomarkers Prep B2.5		X ^a	X			X		X	X	X
Serum IgE		X ^a	X			X		X	X	X

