A starting dose of 0.3 mg PF-07242813 IV is planned. The predicted PF-07242813 C_{max} and AUC_{168H} at the 0.3 mg single dose are approximately 10890-fold and 11150-fold, respectively, below the exposure limits pre-defined for PF-07242813 dose escalation (see Table 4). The predicted exposures at the 0.3 mg single dose are approximately 39- and 82-fold below the steady-state exposure at projected efficacious dose (30 mg SC Q4W) for C_{max} and AUC_{tau} ($\tau=4$ weeks/672 hrs), respectively. The maximum CD1a receptor occupancy at skin, the site of action after 0.3 mg IV single dose is predicted to ~29%, at which level little pharmacological effect is expected as PF-07242813 is an antagonist of CD1a target engagement. The starting dose selection is consistent with the EMA guideline on first-in-human study (EMA Guideline on strategies to identify and mitigate risks for first-in-human and early clinical trials with investigational medicinal products) and a recent white paper on FIH starting dose selection by the IQ consortium (Leach et al. 2020).¹⁴ The highest proposed IV infusion dose of 1000 mg is estimated to provide an exposure margin of 3.3-fold for both C_{max} and AUC_{168H} , relative to the exposure limits.

Table 4. Projected Exposures, Maximum CD1a Receptor Occupancy and Safety Margins Following Single IV Doses of PF-07242813^a

DOSE (mg)	C_{max} (μ g/mL)	AUC_{168H} (μ g·h/mL)	$SM_C_{max}^b$ (fold)	SM_AUC^b (fold)	RO ^c (%)
0.3	0.09368	9.51	10890	11150	29.3
1	0.3111	31.65	3279	3349	59.2
3	0.9332	94.95	1093	1116	81.2
10	3.111	316.5	328	335	93.8
30	9.332	949.5	109	112	97.9
100	31.11	3165	33	33	99.4
300	93.32	9495	11	11	99.8
1000	311.1	31650	3.3	3.3	99.9

a. Human PK was predicted using 2-CM model with IV infusion and linear PK. For dose <1 mg, infusion over 10 min, otherwise, infusion over 1 hour. $V_c=3.2$ L, $V_p=2.2$ L, $CL=0.25$ L/day, $Q=0.45$ L/day. For dose <1 mg, it is assumed that infusion over 10 min, otherwise, infusion over 1 hour.

b. SM= safety margin, which is calculated relative the exposure limit ($C_{max} = 1020 \mu$ g/mL and $AUC_{168H}=106000 \mu$ g·h/mL), determined as 1/10th of the mean exposure at NOAEL of 200 mg/kg/week IV in pivotal 13-week cynomolgus monkey toxicity study.

c. A site of action model was used to predict CD1a receptor occupancy at skin with the predicted human PK.

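### The review gate for setting the optional Cohort 14 dose names Day 22 as 7 days after the third dose, but the third dose is on Day 29

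*Protocol*

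**What the plan says.** Section 4.1.1 of the protocol has two review gates for the multiple-dose cohorts.

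- The general rule for moving to the next multiple dose requires, among other things, "Safety/tolerability data through Day 22 (7 days following the 2nd dose) of the ongoing MAD cohort".
- The rule specific to Cohort 14, the optional fifth multiple-dose cohort, makes the dose level depend on "a review of the cumulative safety and PK data up to 1000 mg IV single dose cohort" and on data "at least through Day 22 (7 days following the 3rd dose) of the ongoing 300 mg MAD cohort". It caps the dose at 1000 mg IV.

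The MAD Schedule of Activities (Section 1.2, Table 2) heads its second block "Day 14 Through Day 22 Visits (2nd Dose" and its third block "Day 28 Through Day 99 Visit (3rd Dose". The ECG footnote to the third block fixes the third dose by describing triplicates from "Day 29 prior to dose and up to 48 hours post-dose". The same block contains a Day 36 visit with a window of ±1 day.

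**The concern.** The Cohort 14 gate defines one review point in two incompatible ways, and it cannot be followed as written. It is a decision rule, not background text: it fixes the minimum repeat-dose evidence needed before choosing a dose of up to 1000 mg IV given three times to healthy volunteers.

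If Day 22 governs, the dose may be set before anyone in the 300 mg SC cohort has had a third dose. If the dose number governs, third-dose data from that cohort are required. The sponsor and the investigator could each defend a different gate from the same sentence. The written criterion carries more weight here because sentinel dosing is specified only for the single-dose cohorts (Sections 4.1.1 and 4.2.1) and the study has no data monitoring committee (Section 9.6).

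**Working it through.** **1. Calendar**

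Inputs: dosing every 2 weeks for three doses (Section 4.1.1), first dose on Day 1, and the dose days in Table 2.

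- Dose k falls on Day 1 + 14(k − 1), which gives Days 1, 15 and 29.
- Second dose + 7 days: 15 + 7 = Day 22. This reproduces the general rule.
- Third dose + 7 days: 29 + 7 = Day 36. This does not reproduce the Cohort 14 rule.
- Day 22 relative to the third dose: 22 − 29 = −7, that is, a week before it.
- Difference between the readings: 36 − 22 = 14 days.

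Cross-check: Section 4.2.1 places the Day 99 visit about 70 days after the third dose, and 99 − 70 = 29. Section 4.1.1 also allows other regimens such as every 4 weeks, but less frequent dosing would only move the third dose later than Day 29.

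**2. What the lower-dose cohorts would already show**

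Under the general rule, Cohort 13 (300 mg SC) starts no earlier than Day 22 of Cohort 12 (150 mg SC). When Cohort 13 reaches its Day 22, Cohort 12 is at Day 22 + 21 = Day 43 or later, after its own third dose. The missing third-dose data are therefore those of the 300 mg cohort only, if cohorts run as planned.

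**3. Exposure the Day 22 reading leaves unseen at 300 mg SC**

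Table 5 gives third-dose values only, so the second-dose values come from rerunning its footnoted two-compartment model: Vc 3.2 L, Vp 2.2 L, CL 0.25 L/day, Q 0.45 L/day, absorption rate 0.26/day, bioavailability 60%. The rerun matches the plan's own third-dose figures to about 1%.

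| 300 mg SC Q2W | Cmax (µg/mL) | AUC168H (µg·h/mL) |
|---|---|---|
| Dose 2, model | 39.8 | 6018 |
| Dose 3, model | 48.1 | 7467 |
| Dose 3, Table 5 | 48.1 | 7388 |
| Dose 3 / dose 2, model | 1.21 | 1.24 |
| Dose 2 as share of dose 3 | 83% | 81% |

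**4. Cohort 14 at 1000 mg IV against what has been reviewed**

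Third-dose projections at 1000 mg IV are 441.6 µg/mL and 50640 µg·h/mL (Table 5).

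| Comparator | Cmax ratio | AUC168H ratio |
|---|---|---|
| 300 mg SC, third dose (Table 5) | 441.6/48.1 = 9.2 | 50640/7388 = 6.9 |
| 1000 mg IV, single dose (Table 4) | 441.6/311.1 = 1.4 | 50640/31650 = 1.6 |

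The first row applies on either reading, so it does not measure the discrepancy. The second row is the relevant bridge, because the same sentence requires the 1000 mg IV single-dose data. Section 4.3.2 says of the single dose: "The highest proposed IV infusion dose of 1000 mg is estimated to provide an exposure margin of 3.3-fold". For three IV doses the margins are 1020/441.6 = 2.3 (Cmax) and 106000/50640 = 2.1 (AUC168H).

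**The case against.** The strongest reply is that this is a one-word slip. Cohort 14 is itself a multiple-dose cohort, the general rule uses Day 22 with the second dose, and Table 2 puts Day 22 in the second-dose block. Reading 3rd as a mistake for 2nd gives the general rule and changes nothing in conduct. That is plausible, but it is an inference. The Cohort 14 sentence is a separate gate for the only planned repeat-dose IV cohort, and a stricter third-dose requirement there would be equally coherent.

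The second reply is that little is at stake, and most of this stands:

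- Day 22 is a minimum, and Section 6.6.1 separately requires a satisfactory review of available data before the next dose.
- The first Cohort 14 dose cannot exceed the single 1000 mg IV dose already reviewed. That dose is projected at 311.1/48.1 = 6.5 times (Cmax) and 31650/7388 = 4.3 times (AUC168H) the third-dose exposure of 300 mg SC, so the level of exposure is already covered.
- If Cohort 14 began on Cohort 13's Day 22 and each cohort were dosed together, its second and third doses would fall on Cohort 13's Days 36 and 50. Third-dose data at 300 mg would by then exist, though no formal review is mandated at that point.
- Cohort 14 is optional and has 8 participants, 6 on active drug.

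These points limit the consequence. They do not tell the site which review point to apply.

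**Conclusion.** The concern holds. The stated day and dose number contradict each other on the protocol's own dosing calendar, in current body text, and the documents favour one reading without establishing it.

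The size is 14 days and one of three doses, in the 300 mg SC cohort only. What the Day 22 reading leaves uncovered is repeat-dose accumulation at the highest SC dose, about 1.2-fold in projected exposure. It is not an unbridged jump to 1000 mg IV. The accumulation figure rests on the protocol's assumed linear two-compartment parameters, and the statement about lower-dose cohorts rests on cohorts running in the planned order. The calendar contradiction needs neither assumption.

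This should be corrected because it is an escalation criterion in a first-in-human study, not because the exposure gap is large.

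**What to change.** Amend the one sentence in Section 4.1.1 so that day and dose agree, in one of two ways:

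- Replace Day 22 with Day 36 and keep the reference to the third dose. This secures third-dose data at the highest SC dose before the Cohort 14 dose is set, and it uses the Day 36 ±1 visit already in Table 2.
- If the general multiple-dose rule was intended, keep Day 22 and change 3rd to 2nd.

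The sponsor should say which was meant. I would choose Day 36 as the more cautious gate, but that is a design preference and not something the documents establish.

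The cost is one sentence in a protocol amendment, with no new visit and no change to Section 6.6.1. Day 36 adds at most a 14-day wait for an optional cohort; the second-dose wording adds none.
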